6.4.2.1. Serious Adverse Events

The number and percentage of subjects who experienced an SAE (including the SAEs that led to death) during the study drug period will be summarized by treatment using MedDRA PT nested within SOC. Events will be ordered by decreasing frequency within SOC.

6.4.2.2. Other Significant Adverse Events

The number and percentage of subjects who permanently discontinued from study treatment due to an AE (including AEs that led to death) during the study drug period will be summarized by treatment using MedDRA PT nested within SOC. Events will be ordered by decreasing frequency within SOC.

Fisher's exact test will be performed to compare percentages for each LY3337641 dose group and Placebo at both the SOC and PT levels.

6.4.3. Clinical Laboratory Evaluations

Laboratory analyses will include planned analytes only. Planned analytes are those specified in the protocol. Summaries will be provided in both Système International (SI) and United States (US) conventional (CN) units (when different). Limits from the performing lab will be used to define low and high.

- **Box plots for observed values:** Values at each visit (starting at randomization) will be displayed in box plots for subjects who have both a baseline and a result for the specified visit. Unplanned measurements will be excluded. Baseline will be the last non-missing observation in the baseline period. Original-scale data will be used for the display. These box plots will be used to evaluate trends over time and to assess a potential impact of outliers on central tendency summaries. The box plot will be a notched box for each treatment with outliers displayed, individual measurements outside of reference limits will also be displayed using distinct symbols overlaying the box plot, and descriptive summary statistics will be included in a table below the box plot.
- **Box plots for change values:** Change from baseline to each visit will be displayed in box plots for subjects who have both a baseline and a result for the specified visit. Change from baseline to last observation will also be summarized and analyzed for subjects who have both baseline and at least 1 postbaseline result. Baseline will be the last non-missing observation in the baseline period. The last non-missing observation in the Dosing Period will be used as the last observation. Unplanned measurements will be excluded. The box plot will be a notched box for each treatment with outliers displayed,

change from baseline to last observation will be summarized within the box plot of changes (rightmost column), and descriptive summary statistics will be included in a table below the box plot, along with a p-value using the ANCOVA model containing terms for treatment and the continuous covariate of baseline measurement. Type III sums of squares will be used. The significance of within-treatment group changes from baseline will be evaluated by testing whether the treatment group LSMeans changes from baseline are different from zero using a t-statistic. In addition to the LSMeans and tests, the SD, minimum, Q1, median, Q3, and maximum will be displayed.

- **Outlier/shift displays focusing on low values (where low values are of interest):** A scatterplot, a shift table, and a shift to low table will be created. Unplanned measurements will be included. The scatterplot will plot the minimum value during the baseline period versus the minimum value during the Dosing Period. Lines indicating the reference limits will be included. In cases where limits vary across demographic characteristics, lines indicating the most common limit will be displayed. The shift table will include the number and percentage of subjects within each baseline category (minimum value is low, normal, high, or missing) versus each postbaseline category (minimum value is low, normal, high, or missing) by treatment. Subjects in the safety population will be included in the shift table. The shift from normal/high to low table will include the number and percentage of subjects by treatment whose minimum baseline result is normal or high and whose minimum treatment result is low. Subjects whose minimum baseline result is normal or high and have at least 1 result during the Dosing Period are included. The Fisher's exact test will be used to compare percentages of subjects who shift from normal/high to low between treatments.
- **Outlier/shift displays focusing on high values (where high values are of interest):** The same approach described for low values will be used, except maximum values will replace minimum values.

Alanine aminotransferase (ALT), aspartate aminotransferase (AST), and total bilirubin will not be included in this analysis as different ranges will be used as described in Section 6.4.5.1.

6.4.4. Vital Signs and Body Weight

Blood pressure and pulse will be collected at screening, baseline, and all postbaseline visits.

Body weight will be collected at screening, baseline, and Week 12 or early discontinuation visit (EDV).

- **Box plots for observed values:** To be created as described in Section 6.4.3 for laboratory analyte measurements.
- **Box plots for change values:** To be created as described in Section 6.4.3 for laboratory analyte measurements.
- **Outlier/shift displays focusing on low values:** To be created as described in Section 6.4.3 for laboratory analyte measurements, except the definition of treatment-emergent includes a threshold for change in addition to a limit as described in Table JPDA.6.4. For the scatterplot, the figure will include a line indicating the change threshold in addition to the limit. A treatment-emergent low result is defined as a change

from a value greater than or equal to the low limit at all baseline visits to a value less than the low limit at any time that meets the specified change criteria during the Dosing Period. To assess decreases, change from the minimum value during the baseline period to the minimum value during the Dosing Period will be used.

- **Outlier/shift displays focusing on high values:** The same approach described for low values will be used, except to assess increases, maximum values will replace minimum values. High limits will replace low limits.

Listings will be presented for subjects with treatment-emergent high or low vital signs at any time in the Dosing Period.

Table JPDA.6.4. Categorical Criteria for Abnormal Treatment-Emergent Blood Pressure, Pulse, and Categorical Criteria for Weight Measurement for Adults

Parameter	Low mmHg	High mmHg
Systolic BP (mm Hg) (Supine or sitting – forearm at heart level)	≤90 and decrease from baseline ≥20	≥140 and increase from baseline ≥20
Diastolic BP (mm Hg) (Supine or sitting – forearm at heart level)	≤50 and decrease from baseline ≥10	≥90 and increase from baseline ≥10
Pulse (bpm) (Supine or sitting)	<50 and decrease from baseline ≥15	>100 and increase from baseline ≥15
Weight (kg) (Consistent clothing and timing in relationship to meals and voiding)	(Loss) decrease ≥7%	(Gain) increase ≥7%

6.4.5. Special Safety Topics

In addition to general safety parameters, safety information on specific topics of special interest will also be presented. Topics will be identified by further analysis of laboratory results, and by analysis of AEs, using standardized MedDRA queries (SMQs), Lilly-defined MedDRA PT lists, or a combination of these methods. The primary focus of analyses will be on laboratory test values, where applicable, with a secondary focus on reported AEs related to laboratory values. Additional special safety topics may be added as warranted.

6.4.5.1. Abnormal Hepatic Tests

Analyses for abnormal hepatic tests will involve 4 laboratory analytes: ALT, AST, total bilirubin, and alkaline phosphatase (ALP). In addition to the analyses described in Section 6.4.3, this section describes specific analyses for this topic. The central laboratory reference ranges (CLRM reference ranges) will be used for these laboratory assessments (ALT, AST, total bilirubin, and ALP).

Analyses for change from baseline to last observation, change from the minimum value during the baseline period to the minimum value during the Dosing Period, change from the maximum value during the baseline period to the maximum value during the Dosing Period, and treatment-emergent high or low laboratory results at any time are described in Section 6.4.3.

The subjects with the following abnormal elevations in hepatic laboratory tests at any time will be listed:

- ALT measurement ≥ 3 times, ≥ 5 times and ≥ 10 times the central laboratory ULN in the Dosing Period.
- AST measurement ≥ 3 times, ≥ 5 times and ≥ 10 times the central laboratory ULN in the Dosing Period.
- Total bilirubin measurement ≥ 2 times the central laboratory ULN in the Dosing Period.
- ALP measurement ≥ 1.5 times the central laboratory ULN in the Dosing Period.

6.4.5.2. Rash

Skin rash is an adverse event of special interest (AESI) and will be identified by AE reporting in the AE_RASH eCRF. Rash events will be listed by PT, Common Terminology Criteria for Adverse Events (CTCAE) grade, and relatedness to study drug. SAEs, events requiring interventions regarding study drug (drug interrupted or drug discontinued) and therapeutic interventions will also be reported. The number and percentage of subjects who experienced skin rash as AESI will be provided and compared each dose of LY3337641 and placebo using the Fisher's exact test.

Clinical features of rash will also be listed including presence of skin symptoms (pruritus, burning, skin pain, other) and associated non-skin signs or symptoms as reported by PT, environment exposure, related medical history, and other observation of rash.

6.4.5.3. Potential Myelosuppressive Events

Using clinical laboratory assessments, the potentially drug-related myelosuppressive events of anemia, leukopenia, neutropenia, lymphopenia, and thrombocytopenia will be assessed through analysis of decreased hemoglobin, decreased white cell count, decreased neutrophils absolute count, decreased lymphocytes absolute count, and decreased platelet count, respectively.

Criteria for AE grading from the CTCAE will be applied for laboratory tests related to myelosuppressive events ([Table JPDA.6.5](#)). These CTCAE grading schemes are consistent with both Version 3.0 and Version 4.03 of the CTCAE guidelines. When deriving CTCAE grades for lab analytes with absolute criteria for grading, an adjustment to the CTCAE-defined approach was made. The use of an LLN/ULN from appropriate reference ranges was replaced with a simpler approach that uses a single value (or a sex-specific pair of values for hemoglobin). This adjustment to the CTCAE grading criteria overcomes the irresolute derivation of the grade that can occur when some demographically-specific LLN/ULN values overlap with the CTCAE-defined value that separates normal (Grade 0) and Grade 1.

Treatment-emergent laboratory abnormalities potentially related to myelosuppression occurring at any time during the Dosing Period and shift tables of baseline to maximum during the Dosing Period will be tabulated. Planned and unplanned measurements will be included. A subject listing will also be provided.

Treatment-emergence will be characterized using 5 criteria:

- any increase in postbaseline CTCAE grade from worst baseline grade
- increase to Grade 1 or above at worst postbaseline
- increase to Grade 2 or above at worst postbaseline
- increase to Grade 3 or above at worst postbaseline
- increase to Grade 4 at worst postbaseline.

Table JPDA.6.5. Common Terminology Criteria for Adverse Events (CTCAE) Related to Myelosuppressive Events

Event	Laboratory Test	Grade	Criteria in Système International (SI) Units	Criteria in Conventional (CN) Units
Anemia*	Hemoglobin	0 (normal)	≥ 7.27 mmol (Fe)/L for females and ≥ 8.18 mmol (Fe)/L for males	≥ 12 g/dL for females and ≥ 13.5 g/dL for males
		1	< 7.27 mmol (Fe)/L for females and 8.18 mmol (Fe)/L for males and ≥ 6.2 mmol (Fe)/L	< 12 g/dL for females and 13.5 g/dL for males and ≥ 10 g/dL
		2	< 6.2 mmol (Fe)/L and ≥ 4.9 mmol (Fe)/L	< 10 g/dL and ≥ 8.0 g/dL
		3	< 4.9 mmol (Fe)/L and ≥ 4.0 mmol (Fe)/L	< 8.0 g/dL and ≥ 6.5 g/dL
		4	< 4.0 mmol (Fe)/L	< 6.5 g/dL
Leukopenia*	White blood cell (WBC) count	0 (normal)	≥ 4.0 billion cells/L	≥ 4.0 thousand cells/uL
		1	< 4.0 billion cells/L and ≥ 3.0 billion cells/L	< 4.0 thousand cells/uL and ≥ 3.0 thousand cells/uL
		2	< 3.0 billion cells/L and ≥ 2.0 billion cells/L	< 3.0 thousand cells/uL and ≥ 2.0 thousand cells/uL
		3	< 2.0 billion cells/L and ≥ 1.0 billion cells/L	< 2.0 thousand cells/uL and ≥ 1.0 thousand cells/uL
		4	< 1.0 billion cells/L	< 1.0 thousand cells/uL
Neutropenia*	Absolute neutrophil count (ANC)	0 (normal)	≥ 2 billion cells/L	≥ 2 thousand cells/uL
		1	< 2 billion cells/L and ≥ 1.5 billion cells/L	< 2 thousand cells/uL and ≥ 1.5 thousand cells/uL
		2	< 1.5 billion cells/L and ≥ 1.0 billion cells/L	< 1.5 thousand cells/uL and ≥ 1.0 thousand cells/uL
		3	< 1.0 billion cells/L and ≥ 0.5 billion cells/L	< 1.0 thousand cells/uL and ≥ 0.5 thousand cells/uL
		4	< 0.5 billion cells/L	< 0.5 thousand cells/uL
Lymphopenia*	Lymphocyte count	0 (normal)	≥ 1.1 billion cells/L	≥ 1.1 thousand cells/uL
		1	< 1.1 billion cells/L and ≥ 0.8 billion cells/L	< 1.1 thousand cells/uL and ≥ 0.8 thousand cells/uL
		2	< 0.8 billion cells/L and ≥ 0.5 billion cells/L	< 0.8 thousand cells/uL and ≥ 0.5 thousand cells/uL
		3	< 0.5 billion cells/L and ≥ 0.2 billion cells/L	< 0.5 thousand cells/uL and ≥ 0.2 thousand cells/uL
		4	< 0.2 billion cells/L	< 0.2 thousand cells/uL
Thrombocytopenia*	Platelet count	0 (normal)	≥ 150 billion cells/L	≥ 150 thousand cells/uL
		1	< 150 billion cells/L and ≥ 75 billion cells/L	< 150 thousand cells/uL and ≥ 75 thousand cells/uL
		2	< 75 billion cells/L and ≥ 50 billion cells/L	< 75 thousand cells/uL and ≥ 50 thousand cells/uL
		3	< 50 billion cells/L and ≥ 25 billion cells/L	< 50 thousand cells/uL and ≥ 25 thousand cells/uL
		4	< 25 billion cells/L	< 25 thousand cells/uL

Abbreviation: Fe = iron.

* CTCAE grading was adjusted by replacing lower limit of normal (LLN) with a single value.

Shift tables will show the number and percentage of subjects based on baseline to maximum grade during the Dosing Period, with baseline grade depicted by the most extreme grade during the baseline period. With each shift table, a shift table summary displaying the number and percentage of subjects with maximum postbaseline results will be presented by treatment group within the following categories:

- Decreased: postbaseline category < baseline category
- Increased: postbaseline category > baseline category
- Same: postbaseline category = baseline category.

Scheduled and unscheduled measurements will be included.

A laboratory-based treatment-emergent outcome related to increased platelet count will be summarized in similar fashion. Treatment-emergent thrombocytosis as a laboratory-based abnormality will be defined as an increase in platelet count from a maximum baseline value $\leq 600,000$ cells/ μL to any postbaseline value $> 600,000$ cells/ μL . A listing of subjects meeting criteria for thrombocytosis by treatment group will be provided. Scheduled and unscheduled measurements will be included.

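### SAP Table JPDA.6.5: no single conversion factor links the SI and conventional anemia cut-offs, so one hemoglobin value can receive two CTCAE grades, and the SAP does not say which column governs

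*SAP*

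**What the plan says.** SAP 6.4.5.3 assesses potentially drug-related anemia through decreased hemoglobin, graded by Table JPDA.6.5. The table has an SI column and a conventional column and states no conversion factor.

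- **Grade 0:** SI, at or above "7.27 mmol (Fe)/L for females and ≥ 8.18 mmol (Fe)/L for males"; conventional, at or above "12 g/dL for females and ≥ 13.5 g/dL for males".
- **Grade 2:** SI, "< 6.2 mmol (Fe)/L and ≥ 4.9 mmol (Fe)/L"; conventional, "< 10 g/dL and ≥ 8.0 g/dL".
- **Grade 3:** SI, "< 4.9 mmol (Fe)/L and ≥ 4.0 mmol (Fe)/L"; conventional, "< 8.0 g/dL and ≥ 6.5 g/dL".

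Grade 1 fills the gap between Grades 0 and 2, and Grade 4 lies below the last Grade 3 limit.

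The same section replaces the laboratory's lower limit of normal with one fixed value, or for hemoglobin one value per sex. The grades feed five treatment-emergence criteria, from any increase over the worst baseline grade up to an increase to Grade 4. They also feed the shift tables from worst baseline grade to maximum grade in the Dosing Period. SAP 6.5.5 carries the safety methods of SAP 6.4 into the long-term extension.

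The nearest rule on units is in SAP 6.4.3: laboratory summaries are given in both systems where they differ. It does not say which system derives a grade.

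**The concern.** Two columns for one grade are harmless only if they are the same cut-offs in different units, which requires one conversion factor to link every pair. Here the Grade 0/1 pairs point to one factor and the lower boundaries to another.

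Two programmers who both follow the table could then derive different grades from the same result. They could report different counts of treatment-emergent anemia and fill different shift-table cells, in Part A, Part B and the extension. A choice of column made after the data are seen would also be a choice between two anemia counts.

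Only anemia is affected. For leukopenia, neutropenia, lymphopenia and thrombocytopenia the two columns are numerically identical, and the creatinine grades in Table JPDA.6.6 are multiples of the upper limit of normal.

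**Working it through.** **Inputs.** All cut-offs come from SAP Table JPDA.6.5. No outside conversion factor is used.

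**Step 1. Factor implied by each pair.** Factor = SI / conventional. If the SI figure was rounded, the allowed interval is (SI ± half its last digit) / conventional.

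| Boundary | SI | g/dL | Ratio | Interval |
|---|---|---|---|---|
| 0/1 women | 7.27 | 12 | 0.6058 | 7.265/12 to 7.275/12 = 0.6054 to 0.6063 |
| 0/1 men | 8.18 | 13.5 | 0.6059 | 8.175/13.5 to 8.185/13.5 = 0.6056 to 0.6063 |
| 1/2 | 6.2 | 10 | 0.6200 | 6.15/10 to 6.25/10 = 0.6150 to 0.6250 |
| 2/3 | 4.9 | 8.0 | 0.6125 | 4.85/8 to 4.95/8 = 0.6063 to 0.6188 |
| 3/4 | 4.0 | 6.5 | 0.6154 | 3.95/6.5 to 4.05/6.5 = 0.6077 to 0.6231 |

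The two 0/1 rows share 0.6056 to 0.6063. The three lower rows share 0.6150 to 0.6188. The intervals do not meet: the 1/2 row needs at least 0.6150 and the 0/1 rows allow at most 0.6063.

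**Step 2. Other rounding conventions.** Neither is stated in the SAP.

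- SI figures truncated: the 0/1 rows share 8.18/13.5 = 0.6059 to 7.28/12 = 0.6067. The lower rows share 6.2/10 = 0.620 to 5.0/8 = 0.625.
- SI figures rounded up: the 0/1 rows share 8.17/13.5 = 0.6052 to 7.27/12 = 0.6058. The lower rows share 6.1/10 = 0.610 to 4.9/8 = 0.6125.

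The intervals fail to meet in both cases.

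**Step 3. Size if the factor fits the lower rows under rounding.** Convert the SI 0/1 limit back to g/dL and subtract it from the conventional limit.

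- Women: 12 − 7.27/0.615 = 0.179; 12 − 7.27/0.61875 = 0.251 g/dL.
- Men: 13.5 − 8.18/0.615 = 0.199; 13.5 − 8.18/0.61875 = 0.280 g/dL.

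A value in this band is Grade 1 by the conventional column and Grade 0 by the SI column. If hemoglobin is reported to 0.1 g/dL (an assumption), the band holds one or two values per sex. At 0.617 these are 11.8 and 11.9 in women, and 13.3 and 13.4 in men.

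Single edge values also differ lower down:

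- 10.0 g/dL converts to 6.15 at 0.615 and to 6.19 at 0.61875. Both are below 6.2, so it is Grade 1 conventional and Grade 2 SI.
- 6.5 g/dL is Grade 3 conventional and Grade 4 SI for factors below 4.0/6.5 = 0.6154.

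**Step 4. Size if the factor is about 0.606.** At 0.606, 12 g/dL converts to 7.272 and 13.5 g/dL to 8.181, so the 0/1 limits agree. The mismatch moves down:

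- 10.0 to 10.2 g/dL (6.06 to 6.18, below 6.2): Grade 1 conventional, Grade 2 SI.
- 8.0 g/dL (4.85, below 4.9): Grade 2 conventional, Grade 3 SI.
- 6.5 and 6.6 g/dL (3.939 and 3.9996, below 4.0): Grade 3 conventional, Grade 4 SI.

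**Step 5. Can any factor give full agreement?** Grading every 0.1 g/dL value from 5.0 to 15.9 by both columns, with unrounded conversion, no factor from 0.600 to 0.630 does. The smallest number of discordant sex-and-value combinations is five. At 0.620, for example, they are 11.8 and 11.9 in women and 13.2, 13.3 and 13.4 in men.

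**The case against.** The best case on the other side accepts the arithmetic and contests its reach.

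**Location.** A reader might infer that the mismatch is mainly at Grade 0 versus Grade 1. The documents do not support that as a flat statement, because they give no factor. At about 0.606 there is no Grade 0/1 mismatch. At 0.615 women have one discordant reportable value at each of the 0/1, 1/2 and 3/4 boundaries. This objection stands.

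**Purpose.** A reader might infer that the table defeats the section's own aim, since the adjustment is said to be one that "overcomes the irresolute derivation of the grade that can occur". That sentence concerns limits of normal that vary by demographic group and overlap the value separating Grade 0 from Grade 1. It does not concern units, so the SAP does not contradict its stated aim. This also stands.

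**Two contradictory tables.** A reader might infer that SAP 6.4.3 forces an SI and a conventional version of each graded table. That rule covers general laboratory summaries, and a grade has no unit, so separate versions are possible but not clearly required.

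**Origin of the lower rows.** SAP 6.4.5.3 describes its scheme as consistent with CTCAE 3.0 and 4.03 and describes only the limit of normal as replaced. The one-decimal SI figures may therefore be inherited. The documents cannot settle this, and it would not make the columns agree.

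**Practical weight.** The safety analyses are described as descriptive (SAP 6.4), and the general shift-to-low tables use the performing laboratory's limits (SAP 6.4.3). Entry excludes hemoglobin below 8.5 g/dL (Protocol 5.2, criterion 15), so the 2/3 and 3/4 edges need a later fall. This limits the importance of the point but does not remove the ambiguity.

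**Conclusion.** The point holds as a minor defect. The two anemia columns are not interconvertible at any single factor, whether the SI figures were rounded, truncated or rounded up, and no passage says which column derives the grade. That conclusion rests on the table alone.

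The size is conditional. The Grade 0/1 bands assume a factor that fits the lower rows under rounding; the downward shift assumes about 0.606. Counts of discordant values also assume reporting to 0.1 g/dL and unrounded conversion.

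A reader might go further and infer a stated share of misgraded subjects or a bias between arms. Neither is supported: the documents give no hemoglobin distribution, and every arm is graded by the same rule. The effect is confined to descriptive anemia grade counts and shift tables. The ACR20 analysis, power and the per-protocol set do not use these grades.

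**What to change.** In SAP 6.4.5.3:

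- Name one governing unit for hemoglobin grading. Derive each grade once in that unit and use it in all outputs, including the extension.
- Either mark the other column as display only, or recompute all of its anemia boundaries from one stated conversion factor and rounding rule.

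The sponsor must say which cut-offs were intended; this review does not choose between them. If the display-only option is taken, the cost is one sentence and one column label. Recomputing means revising the anemia rows of one column. Neither needs new data or a protocol change. The decision should be made before grades are derived from unblinded data.

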6.4.5.4. Lymphocyte Subset Cell Counts

The lymphocyte subsets, CD19+B cells and CD20+B cells, will be analyzed. Both the absolute count and the relative count (that is, as a percentage of the total lymphocyte population) will be analyzed. For these parameters, the analyses will be performed using the same approaches as described for analysis of clinical laboratory measurements in Section 6.4.3. For determining treatment-emergent abnormal, high, or low lymphocyte subset cell counts, central laboratory reference ranges will be used when available.

